8.7.4.3 Supportive Analysis

To assess the consistency of the Primary Analysis results, supportive analysis will be conducted using the ITT population. Statistical methodology for the supportive analyses will be the same as that of the primary analysis, with the exception of the analysis population used.

8.7.5 Safety Analysis

The Safety population will be used for the analysis of safety endpoints.

For continuous variables data will be summarized using n, mean, Standard Deviation (SD), minimum and maximum values. For categorical variables data will be summarized using frequency and percentage. No inferential statistics are planned.

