
Statistical Considerations:
 
Sample Size Determination and Rationale:
 
Sample size determination is not applicable as only those subjects who are currently enrolled in PRO 140_CD 01 Treatment Substitution Study are allowed to participate in this extension study.
 
Analysis Populations:
 
The Intent-to-Treat (ITT) population is defined as the set of subjects who have received at least one dose of PRO 140 in the extension study and have at least one post-treatment efficacy assessment for viral load.
	

Name of Sponsor: CytoDyn Inc.	
Name of Study Product: PRO 140 (Humanized monoclonal antibody to CCR5) Comparator: Historical Control	
Protocol Number: PRO 140_CD 01-Extension	Indication: Human Immunodeficiency Virus Type-1 (HIV-1) Infection

The Per Protocol (PP) population is defined as the set of subjects who meet the ITT population requirements, and were not associated with a major protocol violation. This population will be identified before the database lock. The PP population will be the primary analysis population for the analysis of primary and secondary endpoints.
 
The Safety population is defined as all subjects who received at least one dose of PRO 140. This population will be used for the analysis of safety parameters.
	

Interim Analysis:
 
There is no planned interim analysis (IA) for efficacy. IA for safety will be conducted after all enrolled subjects complete extended treatment with PRO 140 or until study treatment is discontinued, whichever comes first.
 
Virologic failure will be reported to the Data Monitoring Committee as the event occurs, allowing the DMC to review interim results and make recommendations to the Sponsor.
	

Statistical Analysis:
 
All data collected from the study will be presented as a by-subject listing and also summarized according to the variable type as:
 
Continuous data summaries will include number of observations, mean, standard deviation, median, and minimum and maximum valuesCategorical data summaries will include frequency counts and percentages	

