8.2.3 Safety Endpoints

Safety measurements will include:

- Tolerability of repeated subcutaneous administration of PRO 140 as assessed by study participants (using Visual Analogue Scale) and by investigator-evaluation of injection site reactions.
- Frequency of Grade 3 or 4 adverse events as defined by the DAIDS Adverse Event scale
- Frequency of Treatment-emergent serious adverse events

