8.6.1.3 Safety Population

The Safety population is defined as all subjects who received at least one dose of PRO 140. This population will be used for the analysis of safety parameters.

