8.7.5.1 Adverse Events

Adverse events will be coded using Medical Dictionary for Regulatory Activities (MedDRA). TEAEs are defined as events with an onset on or after the first treatment. TEAEs will be summarized by treatment group, System Organ Class, and preferred term. The following TEAE summaries will be provided:

- TEAEs by severity grade
- TEAEs by relationship to study treatment.

In addition, separate summaries of SAEs, and AEs resulting in discontinuation of study treatment will be presented.

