8.7.5.6 ECG Examination

All ECG examination findings will be listed and any abnormality will be summarized.

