9.1.3 CTCAE Grade (Severity) Assessment

The investigator will carefully evaluate the comments of each subject and the response to treatment in order to judge the true nature and severity of the AE. The question of the relationship of AEs to study drug should be determined by the investigator after thorough consideration of all available facts. To assess severity, the investigator will use the DAIDS AE grading table (for adverse events as well as any injection site reactions refer to [Section 17.2](#) and [Section 17.3](#)).

If a severity rating is not defined in the DAIDS AE grading table for a particular AE, severity will be rated according to the guidelines outlined in CTCAE v4.03. The general guidelines for assessing the AE grade appear below. Full guidelines may be obtained at <http://evs.nci.nih.gov/ftp1/CTCAE>.

Table 9-1: CTCAE v4.03 General Guidelines

Grade	Description
Grade 1	Mild; asymptomatic or mild symptoms; clinical or diagnostic observations only; intervention not indicated.
Grade 2	Moderate; minimal, local, or noninvasive intervention indicated; limiting age-appropriate instrumental activities of daily living (ADL)*.
Grade 3	Severe or medically significant but not immediately life-threatening; hospitalization or prolongation of hospitalization indicated; disabling; limiting self care ADL†.
Grade 4	Life-threatening consequences; urgent intervention indicated.
Grade 5	Death related to AE.

*Instrumental ADL refer to preparing meals, shopping for groceries or clothes, using the telephone, managing money, etc.

†Self care ADL refer to bathing, dressing and undressing, feeding self, using the toilet, taking medications, and not bedridden.

-Common Terminology Criteria for Adverse Events (CTCAE), v4.03: June 14, 2010

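### Safety summaries are limited to crude percentages despite very unequal exposure, and the analysis-set and ECG wording needs reconciling

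*Protocol*

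**What the plan says.** **Measure.** Protocol Section 8.7.5 states for safety data: "For categorical variables data will be summarized using frequency and percentage". It adds: "No inferential statistics are planned". Two of the safety endpoints in Section 8.2.3 are frequencies: treatment-emergent serious adverse events, and "Frequency of Grade 3 or 4 adverse events as defined by the DAIDS Adverse Event scale".

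**Exposure.** Under the synopsis (Trial Design), treatment continues until the product is approved for marketing or the sponsor withdraws the IND. Section 4.2 ends it earlier at virologic failure and still names a 161-week phase.

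**Populations.** The synopsis restricts the ITT population to subjects who "received at least one dose of PRO 140 in the extension study" and who have a post-treatment viral load. Section 8.6.1.1 asks for a dose and a viral load without the extension qualifier. Section 8.6.1.3, in line with the synopsis, reads: "The Safety population is defined as all subjects who received at least one dose of PRO 140". The per-protocol population in Section 8.6.1.2 is built on the ITT definition and is the primary efficacy population.

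**ECG.** Section 8.5.3 lists ECGs among the data sent to the DMC, and Section 8.7.5.6 says: "All ECG examination findings will be listed and any abnormality will be summarized".

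**The concern.** Long-term safety is the secondary objective in Section 2. In a single-arm study whose subjects may leave after a few weeks or stay for years, the share of subjects with an event reflects both the risk and how long each subject was watched. Exit at virologic failure also ties follow-up to efficacy. A low percentage could mean a safe drug or many early failures, and a reader given only the percentage cannot tell which.

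The population wording matters because everyone who consents has already completed 12 weeks of PRO 140 in CD 01 (Section 3.3.1). A condition of one dose of PRO 140 therefore excludes nobody. The denominator of every safety percentage, and membership of the ITT and per-protocol sets, then depends on how the sentence is read. The ECG text promises the DMC a data type that the protocol does not schedule.

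**Working it through.** The protocol states no safety rate, so there is no figure of its own to reproduce.

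**1. Crude percentage against follow-up**

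Inputs: the longest phase length that the protocol names is 161 weeks (Section 4.2), and the planned number is up to 28 subjects (synopsis). The event rates are assumptions, shown over a range.

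Formula: with a constant first-event rate *r* per patient-year and follow-up of *t* years, the expected percentage is 100 × (1 − exp(−*r t*)), with *t* = weeks × 7 / 365.25. So 4, 52 and 161 weeks are 0.077, 0.997 and 3.086 years.

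| Assumed rate per patient-year | 4 weeks | 52 weeks | 161 weeks |
|---|---|---|---|
| 0.05 | 0.4% | 4.9% | 14.3% |
| 0.10 | 0.8% | 9.5% | 26.5% |
| 0.20 | 1.5% | 18.1% | 46.0% |

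The underlying risk is the same along each row.

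**2. Effect of early exit on one overall percentage**

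Take a rate of 0.10, 28 subjects, and exit either at week 12 (0.230 years, 2.3%) or at week 161 (26.5%). The exit shares are assumptions. Results come from unrounded values.

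- All stay: 26.5%, with 28 × 3.086 = 86.4 patient-years of treatment.
- Half exit at week 12: 0.5 × 2.3% + 0.5 × 26.5% = 14.4%, with 28 × (0.5 × 0.230 + 0.5 × 3.086) = 46.4 patient-years.
- Three quarters exit at week 12: 0.75 × 2.3% + 0.25 × 26.5% = 8.3%, with 28 × (0.75 × 0.230 + 0.25 × 3.086) = 26.4 patient-years.

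A rate does not move in this way. Under the same model each subject contributes on average 1 − exp(−*r t*) first events and (1 − exp(−*r t*)) / *r* years at risk, so the ratio is *r* in all three cases: 10 per 100 patient-years.

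**3. Population wording**

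- Section 3.3.1: entry requires 12 completed weeks of PRO 140 in CD 01.
- Section 5.3: a consented subject with a screening number who is not treated is a screen failure. Nothing there removes such a subject from an analysis set.
- Section 8.6.1.3: one dose of PRO 140 suffices. The CD 01 doses meet this literally.
- Section 8.6.1.1: one dose and one post-treatment viral load. Table 4-1 shows PRO 140 and HIV-1 RNA at both screening visits as CD 01 activities, so a screen failure can meet this too. The synopsis definition excludes that subject.

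Illustration, with both counts assumed: 28 consented and 5 with an event give 5/28 = 17.9%. If 1, 3 or 5 of the 28 never received an extension dose, the percentage among those treated is 5/27 = 18.5%, 5/25 = 20.0% or 5/23 = 21.7%.

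**4. ECG**

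Tables 4-1 to 4-9, the visit lists in Sections 4.1 to 4.3 and the procedures in Section 7 contain no ECG. The one other operational mention is in Section 9.3, where an ECG report may be requested as supporting documentation for a serious adverse event.

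**The case against.** The strongest reply is that a percentage of subjects with an event is a valid description in a single-arm, open-label study with no safety inference. Person-time summaries are commonly left to the SAP, to which Sections 8 and 8.6.2 defer the details, and Section 8.7.5 does not forbid them. This stands: the lack of a rate is not an error, and the rates used above are assumptions. What remains is that the protocol itself names the safety measure, and that measure alone serves a long-term objective poorly.

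On populations, the reply is that Section 5.3 uses treated in the sense of treated in the extension, and that screen failures have only a screen-failure eCRF page (Sections 4.1.1 and 11.2), so they would bring almost no data. This limits the practical effect. It does not remove the conflict between Section 8.6.1.1 and the synopsis.

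On ECGs, unscheduled tracings may exist through Section 9.3, so an ECG listing need not be empty. The promise to the DMC still has no scheduled source.

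A reader might also infer that deaths escape safety reporting, since Table 9-1 has a Grade 5, "Death related to AE", outside the Grade 3 or 4 endpoint. The documents do not support that. The endpoint names the DAIDS scale, while Table 9-1 is the CTCAE fallback. Death is a criterion for a serious adverse event (Section 9.2), serious events are a separate endpoint, TEAEs are tabulated by grade (Section 8.7.5.1), and the DMC reviews all deaths (Section 12). Only a wording gap in one endpoint is left.

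**Conclusion.** The point holds as a limit on interpretation plus three consistency faults. The crude percentages are not wrong counts, but at one assumed risk of 0.10 per patient-year they range from 0.8% at 4 weeks to 26.5% at 161 weeks, and the overall figure falls from 26.5% to 8.3% if three quarters of subjects leave at week 12. These sizes rest on a constant rate and assumed exit times. An open-ended phase would widen the range.

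The conflict over the ITT definition, the literal reach of the Safety set and the unscheduled ECG data follow from the text without assumptions. The per-protocol set inherits the ITT wording, so the gap reaches the primary efficacy population, though its likely numerical effect is small.

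A reader might further infer that the TEAE rule, "TEAEs are defined as events with an onset on or after the first treatment", could start the clock at the first CD 01 dose. It does not: Section 4.2 identifies TE1 as the date of first treatment, and Section 9.1.1 starts adverse event reporting at the first treatment visit, which Section 4.2.1 names as TE1.

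**What to change.** - **Section 8.7.5:** keep the counts and percentages. Add total exposure on PRO 140 and, for the adverse event endpoints, subjects with a first event per 100 patient-years at risk on PRO 140, with exact Poisson intervals. The intervals describe precision and involve no test, so they fit a descriptive analysis.
- **Sections 8.6.1.1 and 8.6.1.3, and the Safety definition in the synopsis:** require the dose to have been given in the extension, as the synopsis ITT definition does. The per-protocol set then follows.
- **Sections 8.5.3 and 8.7.5.6:** reconcile with Tables 4-1 to 4-9 and Section 7, so that what is promised to the DMC matches what is collected.
- **Section 8.2.3 and the synopsis (optional):** word the severity endpoint as Grade 3 or higher.

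The cost is a few words in the protocol, matching text in the SAP, one added column in the adverse event tables and minor programming. No new data are needed for the exposure and population changes. What the ECG reconciliation costs depends on how the sponsor resolves it.

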8.7.5.1 Adverse Events

Adverse events will be coded using Medical Dictionary for Regulatory Activities (MedDRA). TEAEs are defined as events with an onset on or after the first treatment. TEAEs will be summarized by treatment group, System Organ Class, and preferred term. The following TEAE summaries will be provided:

- TEAEs by severity grade
- TEAEs by relationship to study treatment.

In addition, separate summaries of SAEs, and AEs resulting in discontinuation of study treatment will be presented.

8.7.5.2 Tolerability Assessment

All data from tolerability assessments of repeated subcutaneous administration of PRO 140 as assessed by study participants (using Visual Analogue Scale) and by investigator-evaluation of injection site reactions will be summarized.

8.7.5.3 Clinical Laboratory Data

All laboratory values will be listed. Laboratory measurements will also be summarized.

8.7.5.4 Physical Examination

All physical examination findings will be listed and any abnormality will be summarized.

8.7.5.5 Vital Signs

All vital sign assessment findings will be listed and summarized.

8.7.5.6 ECG Examination

All ECG examination findings will be listed and any abnormality will be summarized.

8.7.5.7 Neurological Assessment

All neurological assessment findings will be listed and any abnormality will be summarized.

8.7.5.8 Quality of Life Assessment

All quality of life assessment findings will be listed and summarized.

9 ADVERSE EVENTS (DEFINITIONS AND REPORTING)

The Investigator is responsible for the detection and documentation of events meeting the criteria and definition of an AE or SAE, as provided in this protocol. During the study when there is a safety evaluation, the Investigator or site staff will be responsible for detecting, documenting, and reporting AEs and SAEs as detailed in this section of the protocol.

9.1 ADVERSE EVENT

An adverse event (AE) is defined as any unfavorable or unintended sign, symptom, or disease that occurs or is reported by the subject to have occurred, or a worsening of a pre-existing condition. An AE may or may not be related to the study treatment.

AEs will be elicited through direct questioning and subject reports. Any abnormalities in visit evaluations, physical examination findings or laboratory results that the Investigator believes are clinically significant to the research subject and that occurred after initiation of the first study treatment will be reported as AEs. Abnormal findings that are NOT clinically significant (NCS) should not be recorded as an AE.

9.1.1 Reporting of Adverse Events

Report initiation for all AEs and SAEs will begin at the time of the first treatment visit and continue up until the final study visit (i.e. up to NVF-EFU2 for subject who do not experience virologic failure or until viral suppression is achieved for subjects who experience virologic failure). All events will be followed to resolution or until 30 days after the subject completes the study. A final assessment of outcome will be made at that time.

All AEs must be recorded in the subject's medical records and on the eCRFs. AEs will be reported using customary medical terminology along with the following information: the onset and end dates, whether the event is considered to be a SAE (see [Section 9.2](#)), the impact the event had on study treatment (see [Section 9.1.2](#)), the CTCAE grade (intensity) of the event (see [Section 9.1.3](#)), the causality of the event (see [Section 9.1.4](#)), whether treatment was given as a result of the event (see [Section 9.1.5](#)), and the outcome of the event (see [Section 9.1.6](#)).

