- [42] All study subjects will re-initiate their previous antiretroviral regimen: (1) One week prior to the end of Treatment Extension Phase, or (2) Anytime during the Treatment Extension Phase, if virologic failure occurs or have met any other criteria for discontinuation of study treatment as specified in the protocol.
- [43] As assessed by Investigator when study treatment administered at the clinic.
- [44] Subject-perceived injection site pain (average pain since last treatment) will be assessed using the Pain Visual Analog Scale (VAS) prior to each study treatment administration for subjects randomized to PRO 140.
- [45] Should be performed at least once every 12 weeks from TE160 onwards.

Table 4-9: Schedule of Assessments –Follow-Up (FU) Phase

(a) Subjects who do NOT experience virologic failure

Procedure/Assessments	Follow-Up Visit -1	Follow-Up Visit -2
	NVF-EFU1	NVF-EFU2
Window Period	2 weeks (±3 days) after TE161	4 weeks (±3 days) after TE161
Physical Examination	X ^[1]	X ^[1]
Vital Signs	X	X
Plasma HIV-1 RNA level	X	X
TruCount T assay	X	X
Previously used Antiretroviral Regimen	X	X
Adverse Events	X	X
Concomitant Medications	X	X
Anti-idiotypic Antibodies to PRO 140		X

[1] Symptom-directed physical examination

(b) Subjects who experience virologic failure

- Short term follow up visits

Procedure/Assessments	Follow-Up Visit -1	Follow-Up Visit -2	Follow-Up Visit -3 ^[1]
	VF-EFU1	VF-EFU2	VF-EFU3
Window Period	4 weeks (±7 days) after VF	8 weeks (±7 days) after VF	12 weeks (±7 days) after VF
Physical Examination	X ^[2]	X ^[2]	X ^[2]
Vital Signs	X	X	X
Plasma HIV-1 RNA level	X	X	X
TruCount T assay	X	X	X
Previously used Antiretroviral Regimen	X	X	X
Adverse Events	X	X	X
Concomitant Medications	X	X	X
Anti-idiotypic Antibodies to PRO 140	X		

[1] Subject will be followed up every 4 weeks until viral suppression is achieved (i.e., plasma HIV-1 RNA levels to return back to <50 copies/mL). Subject will undergo additional follow-up visits every 4 weeks beyond VF-EFU3 visit, if viral suppression is not achieved at the end of VF-EFU3 visit.

[2] Symptom-directed physical examination

(c) Subjects who experience virologic failure

- Long term follow up visits

Procedure/Assessments	Long-Term Follow-Up Visit -1	Long-Term Follow-Up Visit -2
	VF-12mFU	VF-24mFU
Window Period	12 months (± 1 month) after VF visit	24 months (± 1 month) after VF visit
Assessment of cART changes ^[1]	X	X
Plasma HIV-1 RNA level	X	X
TruCount T assay	X	X

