4.3 FOLLOW-UP PHASE

The duration of follow-up depends on the status of viral load suppression.

- Subjects who experience virologic failure will be followed up every 4 weeks until the viral load suppression is achieved (i.e., plasma HIV-1 RNA levels to return to <50 copies/mL)
- Subjects who do not experience virologic failure at the end of Treatment Extension Period, will be followed up every 2 weeks for total of 4 weeks.
- *Note: Virologic failure subjects will have a long term safety follow up visit once a year within 2 years of completing the last VF-FU visit.*

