4.3.1 Follow-Up Visits

The following assessments will be performed at each follow-up visit, unless otherwise specified:

- Assess for any Adverse Events and changes in Concomitant medications (see [section 9](#) and [7.5](#)),
- Symptom-directed physical examination (see [section 7.6](#)) *at NVF-EFU and short term VF-EFU visits*,
- Vital Signs (see [section 7.9](#)),
- Collection of Blood Specimens (see [section 7.10](#)) for
 - Plasma HIV-1 RNA level
 - TruCount T Assay
 - Anti-idiotypic antibodies to PRO 140 *(NVF-EFU2 and VF-EFU1 visits)*
 - Trofile® DNA or RNA Assay *(VF-12mFU and VF-24mFU visits)*
 - PhenoSense® Entry Assay *(VF-12mFU and VF-24mFU visits)*
 - HIV-1 Drug Resistance Assay *(VF-12mFU and VF-24mFU visits)*

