5 SUBJECT COMPLETION AND WITHDRAWAL

5.1 SUBJECT COMPLETION

- A subject who completes the Treatment Extension Phase (without virologic failure) and 4-week Non-Virologic Failure Follow-Up Phase will be considered as having completed the study.
- A subject who experiences virologic failure during the Treatment Extension Phase, undergoes the VF Visit assessments and is followed up until viral suppression is achieved, will be considered as having completed the study.

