9.3 REPORTING OF SERIOUS ADVERSE EVENTS

The Investigator is required to report all SAEs that occur during the time period specified in [Section 9.1.1](#). Once the Investigator becomes aware of an SAE, he/she must report the SAE to Amarex Safety Department within 24 hours:

The Amarex Medical Monitor may request additional supporting documentation as it becomes available, such as lab reports, ECG reports, discharge summary, hospital notes, etc.

The Investigator is also responsible for reporting all SAEs to the appropriate Institutional Review Board (IRB) in accordance with local laws and regulations. The Investigator is responsible for maintaining documentation in the study file that indicates the IRB has been properly notified. Under 21 CFR 312.32(c), the sponsor is required to notify FDA and all participating investigators in an IND safety report (i.e., 7- or 15-day expedited report) of potentially serious risks from clinical trials or any other source as soon as possible, but no later than 15 calendar days after the sponsor receives

the safety information and determines that the information qualifies for reporting. Participating investigators include all investigators to whom the sponsor is providing drug under any of its INDs or under any investigator's IND (21 CFR 312.32(c)(1)).

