12 DATA MONITORING COMMITTEE (DMC)

The study will be monitored by an independent DMC (DMC) to ensure patient safety and to assess efficacy. The CRO is responsible for the overall management of DMC, including development of its charter and membership selection. The DMC will be managed in conformance with the FDA guidelines for DMC independence, management, and oversight.

DMC will conduct scheduled independent reviews of the data in order to ensure that an ongoing acceptable safety profile is being achieved.

DMC will conduct an independent review after all enrolled subjects complete extended treatment with PRO 140 or until study treatment is discontinued, whichever comes first.

The DMC will consist of at least three independent members (including clinicians with expertise in HIV disease, a psychiatrist and at least one biostatistician) and will review all safety signals including number of virologic rebounds, unexpected AEs, all related AEs, all SAEs, and all deaths during the Treatment and Follow-Up Phases.

The DMC will make the following recommendations at the end of safety evaluation:

- Continue the study as planned;
- Modify the study and continue;
- Terminate the study;
- Gather more data to address a specific safety issue and reconvene;
- Other (e.g., request changes to the protocol and propose sanctions).

The Sponsor retains the responsibility to contact FDA and the final decision regarding the recommendation to continue or to terminate the study.

A further description of the DMC reporting requirements, meeting frequency, and the study stopping/continuation criteria can be found in the DMC charter.

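### After virologic failure, the 12- and 24-month safety visits carry no clear duty to report new SAEs, deaths or AIDS-defining events, and the sections that govern them disagree

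*Protocol*

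**What the plan says.** Five parts of the protocol bear on what is collected after virologic failure.

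- **Purpose and place of the late visits.** Section 4.3 (Follow-up Phase), repeated in section 4, states: "Virologic failure subjects will have a long term safety follow up visit once a year within 2 years of completing the last VF-FU visit". Table 4-9, the schedule for the Follow-up Phase, lists them in part (c) as VF-12mFU and VF-24mFU, the first timed "12 months (± 1 month) after VF visit".
- **What 4.3.1 asks for.** Its list covers each follow-up visit unless otherwise specified and opens with "Assess for any Adverse Events and changes in Concomitant medications". No visit restriction is attached to that item.
- **What Table 4-9(c) schedules.** It has ART changes, HIV-1 RNA and the TruCount assay, plus tropism, entry-inhibitor and drug-resistance assays at the investigator's discretion. There is no row for adverse events or concomitant medications. Parts (a) and (b) have both.
- **When reporting ends.** Section 9.1.1 reports AEs and SAEs "until viral suppression is achieved for subjects who experience virologic failure". Section 9.3 follows it: "The Investigator is required to report all SAEs that occur during the time period specified in" section 9.1.1. Section 5.1 says a failure subject who has the VF Visit and "is followed up until viral suppression is achieved, will be considered as having completed the study".
- **What the DMC is to see.** Section 12 includes "all SAEs, and all deaths during the Treatment and Follow-Up Phases".

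**The concern.** Visits described as safety visits are the only follow-up visits in the schedule without an adverse event item. One section asks for adverse events there, the visit table does not, and the reporting section has already closed the window. A site that follows 4.3.1 will ask about events. A site that works from Table 4-9(c) and 9.1.1 will not, and would be within the protocol. The DMC is promised SAEs and deaths from a phase in which sites may have no duty to send them.

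Section 1.7.1.1 itself names drug resistance, opportunistic infection and clinical progression as possible consequences of rebound off ART. Resistance can be picked up by the optional assays. A death, a hospitalisation or an AIDS-defining illness cannot be read from an RNA or CD4 result. With at most 28 subjects planned, whether a single such event is recorded should not depend on which section the site happened to read.

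**Working it through.** The protocol states no figure to reproduce here. The check compares the texts and then measures the length of the gap.

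**Step 1. Are the late visits part of the Follow-up Phase?** Sections 4 and 4.3 place them under that heading, and the title of Table 4-9 covers part (c). Section 5.1 points the other way, since it treats the subject as complete at re-suppression. The protocol does not settle this, and the reach of the section 12 remit depends on it.

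**Step 2. Does 4.3.1 cover the late visits?** It names VF-12mFU and VF-24mFU for the tropism, entry and resistance assays, so its list does extend to them. It confines the physical examination to the non-failure and short-term failure visits, and the anti-idiotypic antibody sample to two named visits. It attaches no such limit to adverse events. On its face, adverse events are assessed at 12 and 24 months.

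**Step 3. Does anything oblige a site to report what it finds?** Section 9.1.1 lets reporting run to the final study visit, then equates that point with re-suppression for failures, although the last visit scheduled for them is VF-24mFU. Section 9.3 imports the same window for SAEs. The further sentence in 9.1.1, "All events will be followed to resolution or until 30 days after the subject completes the study", and the SAE follow-up rule in 9.3.1 concern the follow-up of events already identified. Neither creates a duty to report an event that begins later.

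**Step 4. Length of the gap.** The protocol does not give the time to re-suppression. Assume 4 to 12 weeks, the span from VF-EFU1 to VF-EFU3 in Table 4-9(b), and take 24 months as 104 weeks after the VF visit.

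Weeks without a duty to report new events = 104 − weeks to re-suppression

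- Re-suppression at week 4: 104 − 4 = 100 weeks; 100/104 = 96%
- Re-suppression at week 12: 104 − 12 = 92 weeks; 92/104 = 88%

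Short-term follow-up continues every 4 weeks until suppression, so slower re-suppression shortens the gap. At week 24, for example, it is 104 − 24 = 80 weeks, or 77%. If the late visits are instead timed from the last short-term follow-up visit, as 4.3 has it, the whole two-year period falls after reporting has closed.

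**Step 5. The anchor dates.** Section 4.3 counts from the last short-term visit and Table 4-9(c) from the VF visit. With that last visit at week 4 to 12, a visit at week 104 after failure falls 92 to 100 weeks after it, which is inside two years. Both texts can be met, so the mismatch is minor.

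**The case against.** The strongest reply is that the cut-off is deliberate. Sections 5.1, 9.1.1 and 9.3 agree with one another: a failure subject completes at re-suppression and reporting ends there. On that view the annual visits are a limited virological check, and 4.3.1 is a generic list that the table narrows under its own proviso. Vital signs support this reading, since they too are unrestricted in 4.3.1 yet absent from Table 4-9(c). The DMC conflict also depends on whether visits after completion belong to the Follow-up Phase, and the detail of DMC reporting sits in a charter that is not at hand.

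Much of this stands. The early close of reporting is a coherent rule, and the proviso in 4.3.1 softens the clash. It does not explain why visits outside the reporting window are called safety visits and placed in the Follow-up Phase, or why 4.3.1 marks its exceptions item by item and marks none for adverse events.

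A reader might also infer more than the text supports:

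- **That late harm is not captured at all.** HIV-1 RNA, CD4 and ART changes are required at both visits and resistance assays are available. Open events are followed. Section 9.1 calls for clinically significant findings after first treatment to be reported as AEs, with no end date in that sentence. What is missing is a clear duty to report new events.
- **That events in failures are under-counted relative to other subjects.** Non-failures are reported only to NVF-EFU2, 4 weeks after the end of treatment. Failures are first seen about 4 weeks after the VF visit and then until suppressed, so their window is about as long or longer.
- **That the secondary objective is undercut.** That objective concerns the safety of continued PRO 140 use. These subjects have stopped it and returned to ART.

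**Conclusion.** The inconsistency is real and worth correcting. Sections 4.3, 4.3.1 and 12 point towards collecting adverse events, SAEs and deaths at the late visits. Table 4-9(c) and sections 5.1, 9.1.1 and 9.3 point away from it. As written, new SAEs, deaths and AIDS-defining events after re-suppression carry no clear reporting duty and may be collected differently by site.

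On the assumed 4 to 12 weeks to re-suppression, the gap is about 92 to 100 of the 104 weeks after failure. This measures time without a duty. It says nothing about how many events would be missed, and no such count can be derived from the protocol. The DMC part of the point holds only if the late visits belong to the Follow-up Phase, as sections 4 and 4.3 and the title of Table 4-9 indicate. The primary efficacy analysis is not affected.

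**What to change.** Reconcile sections 4.3.1, 5.1, 9.1.1, 9.3 and 12 with Table 4-9(c):

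1. Add one row to Table 4-9(c) for SAEs, deaths and AIDS-defining conditions (Appendix I list) since the last visit.
2. Extend the section 9.1.1 window to VF-24mFU for those events only, so that 9.3 follows, and let non-serious AEs continue to close at re-suppression. Limit the adverse event item in 4.3.1 to match at these two visits.
3. State in 5.1 and 12 whether the late visits belong to the Follow-up Phase for DMC purposes.
4. As a minor clean-up, use one anchor date for the late visits in 4.3 and Table 4-9(c).

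The cost is a short amendment and one added question at two visits already scheduled. The downside is a longer SAE reporting duty for sites, up to 24 months after failure.
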